Cover Page: Study Protocol

Protocol Title: Comparison of furosemide alone versus the combination of furosemide and

albumin for diuresis in cirrhotic patients with fluid retention

NCT: 04216784

Document Date: 12/5/2019

I. Abstract:

a. A common complication of the progression of cirrhosis is fluid retention (ascites, edema, or pleural effusion). Loop diuretics are the treatment of choice for fluid retention in cirrhotic patients; however, many of these patients demonstrate diuretic resistance, requiring higher doses of the diuretics to achieve adequate diuresis. The cause of this diuretic resistance is hypothesized to be secondary to hypoalbuminemia which has led some providers to give human albumin in combination with loop diuretics to increase intravascular volume and facilitate diuresis. However, this practice remains controversial because minimal data exists to support its efficacy. The purpose of this study is to compare the efficacy of diuretics alone versus diuretics in combination with albumin in cirrhotic patients presenting with fluid retention.

II. Background and Significance:

a. Accumulation of fluid as ascites, edema, or pleural effusion is common in patients with advanced liver disease. 1 Typically, treatment of fluid retention is extrapolated from the practice guidelines by the American Association for the Study of Liver Diseases (AASLD) for the management of adult patients with ascites due to cirrhosis.² According to these guidelines, first line treatments for management of ascites are cessation of alcohol use (when applicable), restricting sodium and fluid intake, and using diuretics (such as loop diuretics). However, many patients with cirrhosis demonstrate diuretic resistance and require higher doses of these medications to obtain the desired clinical effect. Since hypoalbuminemia is postulated to be one of the causes of diuretic resistance in cirrhotic patients, some providers recommend giving albumin in combination with loop diuretics for the treatment of fluid retention. This recommendation developed from the current understanding of the pathophysiology of liver disease and its effect on intravascular space leading to fluid retention. Despite this common trend in practice, there remains minimal data that compares the efficacy of diuresis using diuretics alone versus the combination of diuretics and albumin.

Currently, there is only one randomized, controlled trial published in 1999 that compared the use of diuretics alone versus the combination of diuretics and albumin in cirrhotic patients.³ This was a single center conducted in Italy where the investigators used potassium canrenoate and furosemide as diuretics in combination with albumin (25%) 12.5 grams daily. The doses of diuretics used were per center protocol and based on patient clinical response. The results from their study showed that the cumulative rate of response to diuretic treatment of ascites was higher (90.5% vs. 74.7%) (p< 0.05) and length of hospital stay was shorter (p< 0.05) in the group of patients that received diuretics and albumin versus diuretics alone. Although the results were favorable with the use of albumin, the external validity of this study is minimal since it was a single center conducted in Italy in 1999.

III. Study Aims

a. The purpose of this single center, prospective study is to compare the efficacy of two strategies for diuresis in patients with cirrhosis, the use of furosemide (Lasix®) alone versus the combination of furosemide (Lasix ®) and albumin (25%).

IV. Administrative Organization

 a. All research regarding this project will be performed at Rush University Medical Center (RUMC). There will be no inclusion of outside study sites, laboratories, or data management centers.

V. Methods and Materials

- a. Trial Design and sample size
 - i. We will perform a single-center, prospective study with data collected as result of standard of care at RUMC. Patients who are 18 years of age and older, have diagnosed cirrhosis, and present to RUMC with fluid retention will be identified by the Hepatology and/or Surgery attending and be screened for inclusion in the study. Each patient will be randomized into one of the two cohorts and will have 50% chance of being placed into either cohort.
 Cohort 1 will receive furosemide (Lasix) 40 to 80 mg IVP BID for at least 48 hours and cohort 2 will receive combination of furosemide (Lasix) 40 to 80 mg
 - ii. A sample size of 150 patients for this study was estimated based on the previously published study by Gentilini P and colleagues.³ The estimation was based on a success rate of 70% in patients receiving diuretics alone and 90% in patients receiving diuretics plus albumin (alpha = 0.05; beta =0.25).

IVP BID and albumin (25%) 12.5 grams BID for at least 48 hours.

b. Process of Consent

i. This study is a prospective study so consent from the patient will be obtained prior to enrollment. To obtain consent, the physician will explain the purpose of the study, associated risk and benefits, and answer any additional questions or concerns the patient may ask. If patient decides to enroll in the study, the physician will provide them with the appropriate consent form and all signed forms will be in a securely locked filing cabinet.

c. Participants

i. Adult patients (age ≥18 years old) who have cirrhosis and present to RUMC with fluid retention (ascites, edema, or pulmonary effusions).

d. Inclusion/Exclusion Criteria

 Inclusion criteria: Adult patients (age ≥18 years old), diagnosis of cirrhosis and presents with fluid retention as defined as ascites, edema, or pulmonary effusions requiring diuresis.

ii. *Exclusion criteria*: Patients who are younger than 18 years of age or currently pregnant or who presents with a serum creatinine greater than 2 mg/dL will be excluded.

e. Outcomes

- i. *Primary outcome*: Urine output greater than or equal to 0.5 ml/kg/hour over 24 hours or reduction in weight defined as weight loss of 1 kilogram or greater in a 24-hour period. (While urine output is the best measure for diuretic efficacy, it can often be an unreliable measurement due to patient's not collecting urine properly. Therefore, changes in weight after initiation of diuretic therapy is often used as a surrogate marker for the efficacy of the diuretic therapy, regardless of patient weight at baseline. Several heart failure trials use a change in weight as the endpoint for assessing diuretic efficacy, and this endpoint is also commonly used in clinical practice. Therefore, that is why this endpoint was chosen for this study.)
- ii. **Secondary outcome:** Change in renal function as defined by a chance in serum creatinine from admission to discharge, hospital length of stay, 30-day readmission rates, and patient survival at 6 months and 1 year.

VI. Risk/Benefit Assessment

a. Potential Risks

This study is a prospective trial however minimal risk to the patient is associated with participation in this study as he/she will be receiving one of two standard of care treatments at our center. Minimal risks associated with the study include experiencing common side effects from the FDA-approved medications used for treatment. The most common side effects of furosemide administered intravenously are low blood pressure, dizziness, headache, or irritation of the skin at the site of injection. In addition, the most common side effects of albumin administered intravenously are high blood pressure, headache, nausea/vomiting or irritation of the skin at the site of injection. There is also a potential risk for invasion of privacy since medical records will be accessed but all data will be de-identified to limit the chance of exposure of PHI.

b. Protection against risks

Physicians will be assessing patients in the study daily and will take precautions against the potential common side effects associated with the FDA-approved medications in this study as stated previously. Precautions include daily monitoring of patients through labs and physical examination and making medical interventions as deemed appropriate.

Data will be collected from the electronic medical record which will be de-identified and maintained in Research Electronic Data Capture (RedCap).

c. Potential benefits to subjects

Patients may benefit from taking part in this study. Based on experience with the use of furosemide (Lasix) and albumin in patients with similar conditions, researchers believe it

may be of benefit to people with cirrhosis. However, because individuals respond differently to therapy, no one can know in advance if it will be helpful for these patients. If the current therapy is not deemed helpful by the physician, the physician will start an alternative standard of care treatment for the patient.

d. Alternatives to participation

Patients may choose to not participate in this study. If participants choose to not participate in this study, the physicians will determine an alternative treatment plan for their fluid retention.

VII. Confidentiality of data and information storage

a. Data collection will take place on a data collection tool, which will be separate from PHI and will not contain identifiers. RedCAP will be used for data collection and storage. Patient confidentiality will be maintained by recording only de-identified data onto the data collection form. Although the data collected and stored in REDCap will be exported for analysis, the exported data will contain no unique, patient-identifying information. Access will only be available to the research investigators.

Data collected from the electronic medical record at RUMC will include:

- 1. Patient demographics
- 2. Daily lab results including chemistry panel, INR, liver function tests, renal function tests
- 3. Physician's rating of patient's edema (if applicable)
- 4. Dose, frequency, and administration of furosemide (Lasix ®) and/or albumin

VIII. Analysis Plan

a. Statistical analysis will be performed with SPSS statistical package. Patient characteristics will be described using frequencies, means ± standard deviations or medians ± interquartile ranges. Student's t-test will be used to compare continuous variables. Comparisons between groups or categories will be made using chi-squared test. The threshold for statistical significance will be p<0.05.

IX. Literature Cited

- 2. American Association for the Study of Liver Diseases (AASLD): Practice guidelines for the management of adult patients with ascites due to cirrhosis 2012. Hepatology 57(4), 2013.

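### The starting furosemide dose is open within 40-80 mg in both arms and can be chosen with the allocation known, so it can depend on the arm

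*Combined protocol and SAP*

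**What the plan says.** Section V.a.i sets the treatments. For the control arm: "Cohort 1 will receive furosemide (Lasix) 40 to 80 mg IVP BID for at least 48 hours". For the other arm: "cohort 2 will receive combination of furosemide (Lasix) 40 to 80 mg", on the same schedule, plus albumin (25%) 12.5 g BID. The range is two-fold and identical in both arms. No criterion such as weight, creatinine or home dose governs the choice within it.

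The only text on allocation, in the same section, is that each patient is randomized with an even chance of either cohort. The document mentions no placebo, sham infusion, blinding or concealment, and gives no order for dose choice and randomization.

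The primary outcome (section V.e.i) is met by "Urine output greater than or equal to 0.5 ml/kg/hour over 24 hours" or by "reduction in weight defined as weight loss of 1 kilogram or greater in a 24-hour period".

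Two statements bear on how dosing should be read. The aim (section III) is "to compare the efficacy of two strategies for diuresis in patients with cirrhosis". Of the reference trial, section II says: "The doses of diuretics used were per center protocol and based on patient clinical response".

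The data list in section VII includes "Dose, frequency, and administration of furosemide". Section VIII plans t-tests and chi-squared tests in general terms and does not name dose as something to report or compare.

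**The concern.** Randomization balances the patients. It does not balance a co-treatment chosen afterwards by someone who knows the arm. The prescriber is presumably the treating physician, who will see whether albumin is ordered.

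Furosemide acts directly on both components of the primary outcome. The protocol itself treats dose as relevant: section I describes resistant patients as "requiring higher doses of the diuretics to achieve adequate diuresis". A physician who believes albumin helps might start higher when albumin is absent, which would hide an albumin effect. Another might be more aggressive when albumin is given, which would add to it. In either case the difference between arms would mix albumin with furosemide dose.

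The starting dose is the part of dosing that is hardest to defend as response-driven. No response has been seen when it is chosen, so it can reflect only the patient and, if known, the arm.

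**Working it through.** **What the text settles.** Four facts together make an arm-dependent starting dose possible: the same open range in both arms, no selection rule, no blinding or placebo, and no statement that the dose precedes allocation. No calculation is needed for this part.

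**What the text does not settle.** The documents give no dose-response between 40 and 80 mg and no dosing by arm. Everything below on size rests on assumed values.

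**Inputs from section V.a.ii:** success 70% with diuretics alone and 90% with albumin, alpha 0.05, beta 0.25 (planned power 75%), 150 patients. Assumed here: 75 per arm, a two-sided test, and the normal approximation to the uncorrected chi-squared test.

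**The plan's own figure.** n per arm = [1.96 × √(2 × 0.80 × 0.20) + 0.674 × √(0.70 × 0.30 + 0.90 × 0.10)]² / 0.20² = 54.6, so 55 per arm and 110 in total. The stated 150 does not reproduce from the stated inputs; it is larger than they require. That is a separate matter. Its relevance here is that 75 per arm leaves some margin above 75% power.

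**Power at 75 per arm, no shift.** SE under the null = √(2 × 0.80 × 0.20 / 75) = 0.0653. SE under the alternative = √((0.21 + 0.09) / 75) = 0.0632. Power = Φ[(0.20 − 1.96 × 0.0653) / 0.0632] = Φ(1.138) = 87.2%.

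**Shift from dose.** Shift = (difference between arms in the share starting on the upper dose) × (gain in success on the upper dose). With imbalances of 0, 10, 20 and 30 points and gains of 0, 5, 10 and 20 points there are 16 combinations, with shifts from 0 to 6 points. The largest is 0.30 × 0.20 = 0.06.

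**Power when the shift works against albumin.** The same formula depends on which arm is moved:

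| Shift (points) | Furosemide-alone arm raised | Power | Albumin arm lowered | Power |
|---|---|---|---|---|
| 0 | 70 v 90 | 87.2% | 70 v 90 | 87.2% |
| 1 | 71 v 90 | 84.3% | 70 v 89 | 82.9% |
| 2 | 72 v 90 | 80.9% | 70 v 88 | 77.8% |
| 3 | 73 v 90 | 77.0% | 70 v 87 | 72.1% |
| 4 | 74 v 90 | 72.7% | 70 v 86 | 66.0% |
| 6 | 76 v 90 | 62.9% | 70 v 84 | 53.1% |

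Power crosses 75% at about 3.5 points in the first case (2 of the 16 combinations lie beyond it) and at about 2.5 points in the second (3 of 16). For the first case, exact binomial enumeration puts the crossing at 3.9 points.

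**Rejection when albumin has no effect.** With one arm at 70% and the other raised by 0, 1, 2, 4 or 6 points, the two-sided rejection rate is 5.0%, 5.2%, 5.8%, 8.4% and 13.1%.

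**The case against.** The strongest reply is that dose is part of the treatment being compared. The aim speaks of strategies, and the reference trial dosed on clinical response. A physician who starts lower because albumin is also given, within the permitted range, may simply be applying the combination strategy. This stands for titration after a response has been seen, and the point does not extend to it. It is weaker for the starting dose: nothing says that dose is meant to differ by arm, and the identical ranges suggest it is not.

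A second reply is that dose is already collected and the general tests could compare it by arm. That is correct, and an imbalance could be seen. It could not be undone afterwards.

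A third is that other routes stay open. Section VI.b leaves further interventions to the physician's judgement, and section VI.c allows a switch to another standard treatment. That also stands: fixing the starting dose closes one route, not all of them.

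A reader might infer that the dose should be held for the whole first 24 hours. With BID dosing that would restrict a second dose which can legitimately follow response, so it goes further than this concern supports. A reader might also want to settle here which 24-hour period counts for the primary outcome. It is indeed not located within a course of at least 48 hours, but that is a separate question of endpoint definition, and changing it could affect the 70% and 90% inputs.

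**Conclusion.** The concern holds in a limited form. As written, the plan allows the starting furosemide dose to be chosen with the arm known, and that dose bears directly on the primary outcome.

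A reader might go further and infer that the result will be biased, or biased towards albumin. The documents do not support either: they show an opportunity, with no evidence on whether it would be used or in which direction.

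The size is illustrative. Shifts of 1 or 2 points change little. The shift that brings power below 75% depends on which arm moves, so the 3.5-point figure must not be quoted without the 2.5-point one. The 6-point case needs both a 30-point dose imbalance and a 20-point gain from dose alone, a gain as large as the whole effect the trial is sized on. This is a low-cost improvement worth considering, not a fault that invalidates the design.

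**What to change.** 1. Before the allocation is released, the physician selects the starting furosemide dose within 40-80 mg and records it in REDCap.
2. Treatment starts at that dose in either arm unless a documented safety reason requires otherwise.
3. Later titration on response stays free, as part of each strategy.
4. Delivered furosemide per 24 hours, and departures from the recorded starting dose, are tabulated by arm beside the primary result.

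The cost is one REDCap field, one descriptive table, a slightly earlier dose decision, and a step that releases the allocation only after the dose is entered. That step is new, since the protocol describes no concealment. The dose range, the chi-squared test and the sample size do not change. The fix does not supply blinding: later dose changes made with the arm known would be shown, not prevented.

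### The 70% v 90% planning rates match neither the 74.7% v 90.5% reported for the trial they are credited to nor the stated 150 patients and beta of 0.25

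*Combined protocol and SAP*

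**What the plan says.** Section V.a.ii ties the size to one source: "A sample size of 150 patients for this study was estimated based on the previously published study" (reference 3). The next sentence gives the inputs: "The estimation was based on a success rate of 70% in patients receiving diuretics alone and 90% in patients receiving diuretics plus albumin", with "alpha = 0.05; beta =0.25".

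Section II cites the same reference and reports its result: "the cumulative rate of response to diuretic treatment of ascites was higher (90.5% vs. 74.7%) (p< 0.05". It presents this as the sole trial of the question: "there is only one randomized, controlled trial published in 1999 that compared the use of diuretics alone versus the combination".

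On the remaining inputs, V.a.i says each patient "will have 50% chance of being placed into either cohort", so 150 means 75 per arm. Section VIII names the chi-squared test for categorical comparisons and says "The threshold for statistical significance will be p<0.05". It does not state sidedness or whether a continuity correction applies. No dropout allowance is given with the sample size.

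**The concern.** Two pairs of response rates hang on one reference, and they differ. Rounding could turn 90.5% into 90%, but 74.7% rounds to 75%, not 70%. The protocol names no other source, no local data and no argument for 70%.

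The printed rates also fail an internal check, because 70% v 90% with the stated alpha and beta does not lead to 150. What is at stake is whether the design can be read: the stated effect, its credited source, the sample size and beta cannot all be right together, so the difference the trial was built to detect is unclear.

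**Working it through.** **Inputs.** Section V.a.ii: N = 150, rates 0.70 and 0.90, alpha 0.05, beta 0.25. Section V.a.i: 1:1 allocation, so n = 75 per arm. Section II: source rates 0.747 and 0.905. Section VIII: chi-squared test. Two-sided testing is my assumption. z(0.975) = 1.960 and z(0.75) = 0.674.

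**Step 1: the differences.**
- Plan: 90 − 70 = 20.0 points.
- Source: 90.5 − 74.7 = 15.8 points.
- Gap: 4.2 points. The control rate falls by 4.7, which widens the difference; the albumin rate falls by 0.5, which narrows it. 4.7 − 0.5 = 4.2.
- Ratio: 20.0 / 15.8 = 1.27.

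**Step 2: try to reproduce 150 from the printed inputs.** Let d be the difference, V = p1(1 − p1) + p2(1 − p2), and p̄ the mean rate.
- Unpooled: n = (1.960 + 0.674)² V / d² = 6.940 × 0.300 / 0.0400 = 52.1, so 53 per arm and 106 in total.
- Pooled: n = [1.960 √(2p̄(1 − p̄)) + 0.674 √V]² / d², with p̄ = 0.80. This is [1.960 × 0.5657 + 0.674 × 0.5477]² / 0.0400 = 54.6, so 55 per arm and 110 in total.
- With continuity correction, 130 in total. Exact Fisher, about 124 to 128. One-sided pooled, 86 without and 104 with correction.

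None of these gives 150. Getting from 110 to 150 would take a dropout allowance of 1 − 110/150 = 27%, and none is stated.

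**Step 3: the same formulas at the source's rates.** Here d = 0.158, V = 0.2750 and p̄ = 0.826.
- Unpooled: 6.940 × 0.2750 / 0.02496 = 76.4, so 77 per arm and 154 in total.
- Pooled: [1.960 × 0.5361 + 0.674 × 0.5244]² / 0.02496 = 79.0 (79.02), so 80 per arm and 160 in total.
- Arcsine: 152 in total. With continuity correction, 184.

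**Step 4: power with 75 per arm.** Pooled formula: Φ{[d√75 − 1.960 √(2p̄(1 − p̄))] / √V}. The exact rows enumerate all outcomes of two binomials with n = 75.

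| Method | 70% v 90% | 74.7% v 90.5% |
|---|---|---|
| Pooled normal formula | Φ(1.138) = 87.2% | Φ(0.605) = 72.8% |
| Unpooled normal formula | Φ(1.202) = 88.5% | Φ(0.649) = 74.2% |
| Exact, uncorrected chi-squared | 88.5% | 74.5% |
| Exact, continuity-corrected or Fisher | 83.7% | 66.4% |

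The stated beta of 0.25 means 75% power. With the uncorrected test, the source's rates come close to that at N = 150. The printed rates exceed it by 12 to 14 points.

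**The case against.** Planning rates need not equal a source's observed rates. V.a.ii says the size was estimated on the basis of the earlier study and then states its own rates openly; it does not say that study observed 70% v 90%. Nor is 74.7% v 90.5% a proven benchmark here. Section II calls the source's external validity minimal, its diuretic regimen and albumin schedule differed, and its figure is a cumulative response rate for ascites. This trial uses a 24-hour urine output or weight criterion in patients with ascites, edema or effusions. All of that stands. But none of it is offered as a reason for 70%, and it does not explain why the printed rates disagree with the printed N and beta.

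A reader might infer four stronger things that the documents do not support.
- **That 150 is too small because the effect was inflated.** At the source's rates, 150 gives close to the promised 75% power with the uncorrected test.
- **That the risk of missing the effect doubles, from about 12% to about 26%.** The plan promises 25%, not 12%. The 12% arises only because 150 exceeds what 70% v 90% requires.
- **That results will be interpreted against an overstated effect.** Section VIII relies on a chi-squared test at p<0.05, and no passage uses the 20-point difference to interpret a result.
- **That the calculation was really run at 74.7% v 90.5%.** The fit is suggestive, but no record of the calculation is given.

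**Conclusion.** The point holds as an inconsistency in the stated design. The printed rates differ from those reported for their credited source (20.0 v 15.8 points), without explanation, and they do not yield 150 at beta 0.25 (about 106 to 110 would do). At N = 150 the power is about 87% to 88.5% for the printed rates and about 73% to 75% for the source's rates, against a stated 75%.

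These figures assume two-sided alpha 0.05, 75 evaluable patients per arm and an uncorrected chi-squared test. With a continuity correction or Fisher's test they fall to about 84% and 66%. The discrepancy between the two pairs of rates depends on none of these assumptions. The sample size and the analysis are not shown to be wrong; the stated basis for the size needs correcting.

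**What to change.** Keep N at 150 and revise V.a.ii as follows.

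1. Confirm from the planning record which rates, formula, sidedness and dropout allowance produced 150. The source's rates should not be substituted without this, since that would record inputs nobody has confirmed.
2. If 70% was deliberate, say that it is an assumption not taken from the cited trial, and give the reason. If it was not, state 74.7% v 90.5%.
3. Replace the single beta with the power at both pairs, for example: *With 150 patients (75 per arm), two-sided alpha 0.05 and an uncorrected chi-squared test, power is about 88% for 70% v 90% and about 74% for 74.7% v 90.5%.* If a corrected or exact test is intended, use about 84% and about 66% instead.

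The cost is a few lines of text, with no extra patients and no change to the analysis. The downside is that the power shown for the source's effect falls slightly below the 75% now stated, and further below it if a corrected test is used.

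### The sample size of 150 does not follow from the stated inputs (70% v 90%, alpha 0.05, beta 0.25), and no attrition allowance is stated to explain the gap

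*Combined protocol and SAP*

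**What the plan says.** The whole justification for the trial's size is in section V.a.ii of the protocol. It states: "A sample size of 150 patients for this study was estimated". It names the 1999 Italian trial as the source and gives the inputs as a "success rate of 70% in patients receiving diuretics alone and 90% in patients receiving diuretics plus albumin (alpha = 0.05; beta =0.25". Beta of 0.25 means 75% power.

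Three other places bear on the calculation:

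- Section V.a.i fixes 1:1 allocation: each patient "will have 50% chance of being placed into either cohort".
- Section VIII names the test: "Comparisons between groups or categories will be made using chi-squared test". The significance threshold is 0.05. Sidedness and continuity correction are not mentioned.
- Section II reports the cited trial's result: the "cumulative rate of response to diuretic treatment of ascites was higher (90.5% vs. 74.7%) (p< 0.05". These are not the rates used in section V.a.ii.

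No section states an allowance for dropout, withdrawal or patients whose outcome cannot be assessed.

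**The concern.** A sample size statement should let a reader go from the inputs to the number. Here all the inputs are printed, and they lead to a clearly smaller number. Either 150 was built from something not written down (an attrition allowance or different rates), or the printed beta is wrong.

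The stakes are limited but real. The statement is the protocol's only account of what the trial can detect. If recruitment falls short, the team has no stated number of evaluable patients to protect. If the result is null, a reader cannot tell whether the trial was designed with about 75% power or nearer 88%.

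**Working it through.** **Inputs.** Control success p1 = 0.70, treated success p2 = 0.90, alpha = 0.05, beta = 0.25, total 150 (all section V.a.ii). Allocation 1:1, so 75 per arm (V.a.i). Chi-squared test (VIII). Sidedness is not stated: two-sided is taken as the main case and one-sided is also tried.

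The difference is d = 0.20, the mean rate is 0.80, and the variance sum is 0.70×0.30 + 0.90×0.10 = 0.21 + 0.09 = 0.30. The normal quantiles are 1.960 (two-sided 0.05) and 0.6745 (75% power).

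**Step 1: try to reproduce 150 (two-sided, n per arm).**

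- Unpooled: (1.960 + 0.6745)² × 0.30 / 0.20² = 52.05, so 53 per arm, total 106.
- Pooled: [1.960 × √(2×0.80×0.20) + 0.6745 × √0.30]² / 0.20² = (1.1087 + 0.3694)² / 0.04 = 54.62, so 55 per arm, total 110.
- Continuity-corrected: (54.62/4) × [1 + √(1 + 4/(54.62×0.20))]² = 64.23, so 65 per arm, total 130.
- Arcsine: 2 × (1.960 + 0.6745)² / 0.5158² = 52.18, so 53 per arm, total 106.
- Fisher's exact test: exact power is 74.9% at 62 per arm and 76.7% at 64, so roughly 126 in total.

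With a one-sided 0.05 test the totals are 82 (unpooled and arcsine), 86 (pooled) and 104 (corrected). The figure of 150 is not reproduced. The nearest result, 130, is 20 short; the pooled result is 40 short. Raising power to 80% (two-sided) gives 118 to 144, which still does not reach it.

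**Step 2: what 75 evaluable patients per arm give for 70% v 90%, two-sided.**

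The normal approximation is Φ[(0.20 − 1.960 × √(2×0.80×0.20/75)) / √(0.30/75)] = Φ[(0.20 − 0.1280)/0.0632] = Φ(1.138) = 87.2%.

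| Test | Power at 75 per arm |
|---|---|
| Uncorrected, normal approximation | 87.2% |
| Uncorrected, exact binomial enumeration | 88.5% |
| Continuity-corrected, normal approximation | 82.3% |
| Continuity-corrected, exact binomial enumeration | 83.7% |
| Stated in the protocol | 75% |

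Solving each sample size formula for beta at n = 75 gives 0.115 (unpooled), 0.128 (pooled) or 0.177 (corrected), against the printed 0.25.

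**Step 3: the attrition that would close the gap.** 1 − 106/150 = 29.3%; 1 − 110/150 = 26.7%; 1 − 130/150 = 13.3%. At 65 evaluable per arm, exact power is 83.2% uncorrected and 77.5% corrected. An allowance of about 13% therefore fits beta = 0.25 only approximately, and only for the corrected test.

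**Step 4: the cited trial's rates, 74.7% v 90.5% (section II), two-sided, 75% power.** Arcsine 75.96, so 76 per arm, total 152. Unpooled 76.44, so 77, total 154. Pooled 79.02, so 80, total 160. Corrected 91.24, so 92, total 184. Two of these are close to 150. For this effect, 75 per arm gives 72.8% (normal approximation) or 74.5% (exact) uncorrected, and 66.4% (exact) corrected.

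**The case against.** The strongest reply is that the trial is, if anything, larger than it needs to be. For 70% v 90%, 150 patients exceed every version of the requirement, type I error is untouched, and the remedy alters neither enrolment nor analysis. That is a reporting gap, not a design failure. This largely stands, and it limits the weight of the point. It depends, however, on 70% and 90% being the rates behind 150. The cited trial's rates come closer to 150, and with them the surplus disappears.

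A second reply is that 150 may include an attrition allowance; about 13% on top of 130 would do it. That is possible, and beta = 0.25 could then stand. But it is not written, and the allowance needed runs from 13% to 29% depending on the formula.

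A third reply concerns evaluability. Section V.e.i says of urine output that "it can often be an unreliable measurement", but it says so to justify weight loss as an alternative route to success, so poor urine collection does not in itself make a patient non-evaluable. That is fair, and the documents give no attrition rate. It does not remove the problem entirely: a patient with unreliable urine collection who loses less than 1 kg would still be hard to classify.

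Finally, at the stated rates the real uncertainty is between about 110 and 130 evaluable patients; 150 enters only if other rates were used. That is correct, and it is why the rates need confirming.

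**Conclusion.** The concern holds. As printed, the sample size and beta do not match. The stated inputs need 106 to 130 patients two-sided, fewer one-sided, and 150 evaluable patients give about 84% to 88% power rather than 75%. This rests on 1:1 allocation, as stated, a two-sided 0.05 test, which is assumed, and all 150 patients being evaluable.

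The documents do not show the cause. An unstated attrition allowance, different rates and a wrong beta are all possible. The calculation is therefore not reproducible as written, and that does not show the trial to be too small. For 70% v 90% the discrepancy is conservative; for 74.7% v 90.5% there would be no margin. It should be corrected, but the practical harm is limited.

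**What to change.** Keep 150 and rewrite the sentence in section V.a.ii so that its parts agree. Which wording applies depends on how 150 was obtained, which the sponsor should be able to establish:

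- **All 150 are to be evaluable, rates as stated:** 75 evaluable patients per arm give about 87% to 88% power (beta about 0.12 to 0.13) for 70% v 90% at two-sided alpha 0.05 with an uncorrected chi-squared test, or about 84% if the corrected test is used.
- **150 includes attrition:** state the allowance and the evaluable number it protects (about 27% from 110, or about 13% from 130). Beta = 0.25 can then remain.
- **150 came from other rates:** print those rates with the power they give at 75 per arm.

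In every case, say whether the test is one- or two-sided and whether it is continuity-corrected, and use the same wording in section VIII. The cost is one sentence in the sample size section and a few words in the analysis plan; enrolment and the analysis do not change.
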